9.4.2.1 ECG Data Analysis

ECG data will be presented by individual listings with flagging of values outside the normal ranges and flagging of marked abnormalities. Summary descriptive statistics for the actual values and changes from baseline will be tabulated by nominal time for HR, QRS duration, PR and QTcF. For multiple measurements taken at a nominal timepoint, the average of these measurements will be used as the value at that nominal timepoint in all summaries. In addition, QTcF will be categorized at each timepoint as ≤ 450 ms, > 450 to 480 ms, > 480 to 500 ms and > 500 ms and summarized. Similarly, a summary will be provided of the QTcF changes from baseline at each timepoint categorized as < 30 ms, 30 to 60 ms, and > 60 ms. Changes of the overall ECG interpretation and T-wave and U-wave morphology will be summarized.

9.4.3 Pharmacokinetic Analyses

Analyses will be carried out on the PK analysis set. All PK parameters will be presented by listings and descriptive summary statistics (arithmetic means, geometric means, medians, ranges, standard deviations, and coefficients of variation) separately by group or cohorts.

Individual and mean serum total and active RO7565020 concentration versus time data will be tabulated and plotted on linear or semi-logarithmic scales by dose level, and/or by route of administration in different parts.

PK parameters will be read directly from the serum total and active concentration-time profiles, or calculated using standard non-compartmental methods. The following PK parameters will be computed for RO7565020 as appropriate.

- Time to maximum concentration (t_{\max})
- Maximum serum concentration observed (C_{\max})
- AUC from 0 to last sampling point or last quantifiable sample, whichever comes first (AUC_{last})
- AUC from 0 to infinity (AUC_{inf})
- Terminal half-life ($t_{1/2}$)
- Volume of distribution (V_{ss}) and clearance (CL) (IV only)
- Apparent clearance (CL/F) and apparent volume of distribution (V_z/F) (SC only)

Further data analysis to estimate the dose-exposure relationships and the potential impact of TMDD and of ADAs on PK of RO7565020 will be also conducted as appropriate.

Calculations of additional PK parameters and population pharmacokinetic (popPK) analysis at the end of the dose escalation will be performed as data allow it. Population and individual PK parameters will be estimated, and the influence of various covariates

(such as age, sex, body weight and baseline HBsAg levels [only in Parts 2 and 3]) on these parameters will be investigated in an exploratory way.

The details of the popPK and any other exploratory data analyses will be reported in documents separate from the CSR.

9.4.4 Immunogenicity Analyses

The immunogenicity analyses will include all participants with at least one ADA assessment, irrespective of whether or not the participant receives any treatment ([Shankar et al. 2014](#)).

The numbers and proportions of ADA-positive participants and ADA-negative participants at baseline (baseline prevalence) and after study treatment administration (post-baseline incidence during both the treatment and follow-up periods) will be summarized.

- Participants are considered to be ADA positive if they are ADA negative or have missing data at baseline but develop an ADA response following study treatment administration (treatment-induced ADA response), or if they are ADA positive at baseline and the titer of one or more post-baseline samples is at least 4-fold (e.g., ≥ 0.60 -titer units) greater than the titer of the baseline sample (treatment-enhanced ADA response).
- Treatment-induced ADA responses will be further categorized as either:
 - Transient ADA response: defined as a) ADA negative or no ADA available at baseline, and b) at least one post-treatment ADA-positive sample, and c) only one ADA-positive sample or the time between the first and last ADA-positive sample is less than 16 weeks and d) the last ADA sample is negative
 - Persistent ADA response: defined as a) ADA negative or missing data at baseline, and b) post-treatment ADA-positive samples over 16 weeks or more or the last ADA timepoint is positive ([Shankar et al. 2014](#))
- Participants are considered to be ADA negative if they are ADA negative; if they have missing data at baseline and all post-baseline samples are negative; or if they are ADA positive at baseline but do not have any post-baseline samples with a titer that is at least 4 fold greater than the titer of the baseline sample (treatment unaffected).

The relationship between ADA status and safety, efficacy, PK, and biomarker endpoints will be analyzed and reported descriptively via subgroup analyses.

9.4.5 Pharmacodynamic Analyses

Viral dynamic response analysis will be done for the participants with CHB enrolled in Part 2a, Part 2b, and Part 3, and will be based on the PD analysis set (see [Table 10](#)). Descriptive statistics will be utilized to summarize the viral dynamic response outcome

measure of serum HBsAg and HBeAg (Table 12), and the exploratory viral dynamic endpoints of HBV RNA, HBcrAg, total HBsAg, HBsAg isoform (Table 13).

Table 12 Viral Dynamic Response Statistical Analysis Methods

| Endpoint | Statistical Analysis Methods |
|-------------------------------------|---|
| HBsAg change from baseline | Time course profile: summary descriptive statistics by cohort (including mean, standard deviation, median, minimum, and maximum) (in log10 IU/mL and % change from baseline) at each timepoint. |
| Maximum reduction of HBsAg | Summary descriptive statistics by cohort (including mean, standard deviation, median, minimum, and maximum) (in log10 IU/mL and % reduction). |
| HBsAg loss and HBsAg seroconversion | Proportion of HBsAg loss and HBsAg seroconversion at each timepoint. Percentages are based on PD analysis set. |
| HBeAg loss and HBeAg seroconversion | Proportion of HBeAg loss and HBeAg seroconversion at each timepoint. Percentages are based on PD analysis set. |

Abbreviations: HBeAg = hepatitis B e antigen; HBsAg = hepatitis B surface antigen; PD = pharmacodynamic.

Table 13 Exploratory Viral Dynamic Response Statistical Analysis Methods

| Endpoint | Statistical Analysis Methods |
|---|--|
| Baseline and change from baseline of HBV RNA, HBcrAg, and total HBsAg | Time course profile: summary descriptive statistics by cohort (including mean, standard deviation, median, minimum, and maximum) (in log10 IU/mL) at each timepoint. |

Abbreviations: HBcrAg = hepatitis B core-related antigen; HBsAg = hepatitis B surface antigen; HBV = hepatitis B virus.

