| 8.6 | Anti-Drug Antibody (ADA) ^m | | | | | x ^c | | | | x | x | x | x | x | x | x | x | x | x |
| 8.3.7 | NUC PK | | | | | | | | | | | | | | | | | | x |
| 8.7.4 | Cytokine/Chemokine profile and complement activation (SC5b-9) ^d | | | 3 ^h | x | x | x | x | x | x | x | x | x | x | x | x | x ^o | | |
| 8.7.4 | PBMC HBV-specific cellular immune response ^p | | | x ^c | | | | | | | x | x | x | x | x | x | x | x ^o | |
| 8.7.5 | Clinical Genotyping | | | | | x | | | | | | | | | | | | | |
| 8.7.4 | scRNAseq | | | x ^c | | | | | | | x | x | x | x | x | x | x | x ^o | |
| 8.9 | Research Biosample Repository (RBR) ^q | | | x ^c | | | | | | | x | x | x | x | x | x | x | x | x |
| 8.3 | Adverse Events | | | | | | x | | | | | | | | | | x | x | x |
| 6.5 | Previous and Concomitant Treatments | | | | | | x | | | | | | | | x | x | x | x | x |

Table 3 Schedule of Activities – Part 2 (cont.)

Abbreviations: ADA = anti-drug antibody; AE = adverse event; AFP = α -fetoprotein; AMA = antimitochondrial antibody; ANA = antinuclear antibody; ARFI = elastography/acoustic radiation force impulse; ASMA = anti-smooth muscle antibody; a-TPO = anti-thyroid peroxidase; CRP = C-reactive protein; ECG = electrocardiogram; ET = early termination; HAV = hepatitis A virus; HBcrAg = hepatitis B core-related antigen; HBeAg = hepatitis B e antigen; HBsAb = hepatitis B surface antibody; HBsAg = hepatitis B surface antigen; HBV = hepatitis B virus; HCV = hepatitis C virus; HDV = hepatitis D virus; HEV = hepatitis E virus; HIV = human immunodeficiency virus; MRI = magnetic resonance imaging; NUC = nucleos(t)ide analogue; PBMC = peripheral blood mononuclear cell; PK = pharmacokinetic; RBR = research biosample repository; SAE = serious adverse event; scRNAseq = single-cell RNA sequencing.

- a. If HBsAg value does not return to baseline level on Day 169, participants will come to the clinic for additional follow-up visits every 56 days until HBsAg value returns to < 0.1 log below baseline for two consecutive visits, or up to Day 393, whichever comes first.
- b. Weight and height will be collected during screening period. Weight will be collected in the following visits except Day 2, Day 3, and Day 4 visits.
- c. Assessments or sample collection will be performed at predose.
- d. Unscheduled sample for complement activation and CRP will be collected for suspected immune complex mediated adverse events and other events following Section 8.3.7.

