- e. Vital sign assessments on Days 1: predose, 1 hour postdose, and 4 hours postdose.
- f. Required for Day 337 visit only.
- g. For all women enrolled in the study, blood sample for determining β -human chorionic gonadotropin (HCG) at Screening. Urine pregnancy tests will be performed at specified subsequent visits. If a urine pregnancy test is positive, it must be confirmed by a blood pregnancy test. Pregnancy testing will also be performed whenever a menstrual cycle is missed or when pregnancy is otherwise suspected and according to local practice.
- h. Samples will be collected at predose, then at 4 hours and 8 hours postdose.
- i. In the additional visits, viral resistance sample needs to be collected in the last visit only, i.e., if HBsAg value returns to < 0.1 log below baseline, viral resistance sample needs to be collected in the next confirmation visit.
- j. Liver biopsy or transient elastography/ARFI/MRI results obtained within 6 months prior to study Day 1 are also acceptable.
- k. For all cohorts in Part 2a and Cohorts 1 and 2 in Part 2b, all participants will stay at the clinic for at least 8 hours postdose for safety observation and sample collection. The overnight stay until Day 4 for sample collection and assessment is optional, at the Investigator's discretion. For Cohorts 3 and 4 of Part 2b, all participants will stay at the clinic overnight on Day 1. The overnight stay on Days 2 and 3 for sample collection and assessment is optional, at the Investigator's discretion.
- l. Unscheduled PK sample may be collected according to Section 8.2.3 and Section 8.5, e.g., at the time of treatment discontinuation if an infusion-related AE (such as an injection-related reaction) is reported, or when clinical significant abnormal ECG, an SAE, a severe AE, an AE leading to dose interruption or delay of RO7565020 administration, or an accidental overdose is reported.

Table 3 Schedule of Activities – Part 2 (cont.)

- m. After participants complete the scheduled visits, an additional ADA and PK sample may be collected depending on the emerging ADA data.
- n. PK samples will be collected at predose (2 hours prior to drug administration), then 1 hour (\pm 5 minutes), 4 hours (\pm 15 minutes), and 8 hours (\pm 30 minutes) postdose.
- o. Samples for these tests do not need to be collected if the participant has completed 169 days of follow-up.
- p. Only for participants from selected sites that decide to participate in PBMC collection.

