| 8.5 | RO7565020 PK Sample ^{t,u} | 4 ^v | x | x | x | x | x | x | x | x | x | x | x | x | x | x |
| 8.6 | Anti-Drug Antibody (ADA) ^u | x ^f | | | x | x | x | x | x | x | x | x | x | x | x | x |
| 8.3.7 | NUC PK | | | | | | | | | | | | | | x | |
| 8.7.4 | Cytokine/Cytokine profile and complement activation (SC5b-9) (serum) ^p | 3 ^h | x | x | x | x | x | x | x | x | x | x | x | x ^w | | |
| 8.7.4 | PBMC HBV-specific cellular immune response (blood) ^x | x ^f | | | | | | x | | x | | | | x ^w | | |
| 8.7.5 | Clinical Genotyping | x ^f | | | | | | | | | | | | x ^w | | |
| 8.7.4 | scRNAseq (blood) | x ^f | | | | | | x | | x | | x | x | x ^w | | |
| 8.9 | Research Biosample Repository (RBR) ^y | x ^f | | | | | x | | x | | x | x | x | x | x | |
| 8.3 | Adverse Events | | | | | | x | | | | | | x | x | x | x |
| 6.5 | Previous and Concomitant Treatments | | | | | | x | | | | | x | x | x | x | x |

Table 4 Schedule of Activities – Part 3 (cont.)

Abbreviations: ADA = anti-drug antibody; AE = adverse event; AFP = α -fetoprotein; AMA = antimitochondrial antibody; ANA = antinuclear antibody; ARFI = elastography/acoustic radiation force impulse; ASMA = anti-smooth muscle antibody; a-TPO = anti-thyroid peroxidase; CRP = C-reactive protein; ECG = electrocardiogram; ET = early termination; FU = follow-up; HAV = hepatitis A virus; HBcrAg = hepatitis B core-related antigen; HBeAg = hepatitis B e antigen; HBsAb = hepatitis B surface antibody; HBsAg = hepatitis B surface antigen; HBV = hepatitis B virus; HCV = hepatitis C virus; HDV = hepatitis D virus; HEV = hepatitis E virus; HIV = human immunodeficiency virus; MRI = magnetic resonance imaging; NUC = nucleos(t)ide analogue; PBMC = peripheral blood mononuclear cell; PK = pharmacokinetic; RBR = research biosample repository; SAE = serious adverse event; scRNAseq = single-cell RNA sequencing.

- a. A period refers to the time between one dose of treatment and the start of the next. Up to 6 periods in total.
- b. If HBsAg value does not return to baseline level on Day 169 of the last treatment period, participant needs to come to the clinic for additional follow-up visits every 56 days until HBsAg value returns to < 0.1 log below baseline for two consecutive visits, or up to 56 weeks after final dose, whichever comes first.

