- c. Day 1 refers to the first day of each treatment period. Study day will be calculated on the basis of dosing frequency, e.g., if the dosing frequency is every 28 days, Day 1 of the 2nd treatment period will be Day 29 of study; if the dosing frequency is every 56 days, Day 1 of the 2nd treatment period will be Day 57 of study; if the dosing frequency is every 84 days, Day 1 of the 2nd period will be Day 85 of study. From the second period, for sentinel participants, the whole period can be advanced or delayed by 1 day (i.e., an additional ± 1 day visit window); for non-sentinel participants, the whole period can be advanced by 1 day or delayed by 3 days, (i.e., an additional $-1/+3$ days visit window).
- d. Dose frequency will be determined by emerging Parts 1 and 2 data. Some of these visits will not be needed depending on dose frequency, e.g., if the dose frequency is every 28 days, Day 29 and Day 57 visits will not be needed; if dose frequency is every 56 days, Day 57 visit will not be needed; if dose frequency is every 84 days, Day 29 and Day 57 visits will be needed.
- e. Weight and height will be collected during screening period. Weight will be collected in the following visits except Day 2, Day 3, and Day 4 visits.
- f. Assessments and sample collection will be performed at predose.
- g. Unscheduled sample for complement activation and CRP will be collected for suspected immune complex mediated AEs and other events following Section 8.3.7.
- h. Vital sign assessments on dosing days: predose, 1 hour postdose, and 4 hours postdose.
- i. This assessment will be needed for Day 1 of some intermediate treatment periods only, depending on dose frequency. The minimum testing frequency of this assessment during treatment period is every 12 weeks. Thus, e.g., if the dose frequency is every 28 days, this assessment will be needed for Day 1 of the 4th treatment period; if the dose frequency is every 56 days or every 84 days, this assessment will be needed for Day 1 of every intermediate treatment period.
- j. Required for Day 337 of the last treatment period only.

Table 4 Schedule of Activities – Part 3 (cont.)

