4.2.3 Rationale for Biomarker Assessments

4.2.3.1 HBV Dynamic Biomarkers

RO7565020 is a human IgG1 neutralizing antibody, which showed potent and cross-reactive in vitro neutralization against all main circulating viral genotypes of HBsAg. Therefore, the main virological endpoint in this study relies on measuring HBsAg at timepoints defined in the SoA (Section 1.3).

Additional well-established HBV dynamic biomarkers for the assessment of HBV treatment outcomes will include the time course of anti-HBs levels and the evolution of the HBeAg and anti-HBe statuses. In participants who are HBeAg-positive at study entry, a validated research-use-only (RUO) semi-quantitative calculation may be used to follow the time course of serum HBeAg levels over time. In order to evaluate the formation of HBsAg:HBsAb complexes, an assay is being developed by the Sponsor that may be used to either directly quantify the immune complexes or measure HBsAg independently of the putative formation of complexes (i.e., total HBsAg post-dissociation of HBsAg:HBsAb complexes), as appropriate. Additionally, quantification of HBsAg may be measured using a second assay designed to either evaluate a potential bias of the HBsAg quantitative assay being used or to measure a change in the affinity of RO7565020 to escape mutants that might be selected for by therapy with RO7565020.

Several HBV biomarkers have recently emerged in the field that may further support the demonstration of improved virus control. These novel biomarkers will not be used to screen participants and will not have an impact on any clinical decisions or other endpoint evaluation.

Among these, pregenomic HBV RNA, which bypasses reverse transcription and is released in plasma, may provide a direct measure of the transcriptional activity of cccDNA. Consistent with this view, in NUC-treated participants with suppressed HBV DNA, the presence of detectable circulating HBV RNA signals an increased probability of HBV DNA rebound upon NUC cessation ([Wang et al. 2016](#); [Fan et al. 2020](#); [Seto et al. 2021](#); [Kaewdech et al. 2020](#)). In the course of this study, a validated real-time polymerase chain reaction-based investigational assay may be used to quantify HBV RNA.

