4.3 DURATION OF PARTICIPATION

The duration of each study period is described in [Table 7](#).

Table 7 Duration of Study Periods

| Study Part | Screening | Treatment period | In-clinic period | End-of-study visit*** |
|------------------------|--|------------------|---|--|
| Part 1a | Up to 28 days | Day 1 | Day -1 to Day 4 | 36 weeks after study treatment administration |
| Part 1b | Up to 28 days | Up to 169 days | Day -1 to Day 4, and 1 day after each administration for the following doses, including optional overnight stay* | 36 weeks after the final study treatment administration |
| Parts 2a and 2b | Up to 56 days (Pregnancy testing and liver function up to 14 days) | Day 1 | Day 1** to Day 4, including optional overnight stay* | 24 weeks after study treatment administration (If HBsAg does not return to baseline level at follow-up Week 24, will have additional follow-up visits until returns to <0.1 log below baseline for two consecutive visits, or up to 56 weeks postdose, whichever comes first.) |
| Part 3 | Up to 56 days (Pregnancy testing and liver function up to 14 days) | Up to 337 days | Day 1** to Day 4, and 1 day after each administration for the following doses, including optional overnight stay* | 24 weeks after last study treatment administration (If HBsAg does not return to baseline level at follow-up Week 24, will have additional follow-up visits until return to <0.1 log below baseline for two consecutive visits, or up to 56 weeks post the final dose, whichever comes first.) |

Abbreviations: ADA = anti-drug antibody; HBsAg = hepatitis B surface antigen;

PK = pharmacokinetic.

Note: Participants who permanently discontinue from the study (or study treatment) due to Sponsor's decision (e.g., Sponsor prematurely terminates the study) will undergo safety follow-up for 24 weeks or longer if considered needed by Sponsor on the basis of the emerging data. Every 4 weeks (\pm 3 days) in the first 12 weeks post-final dose, then every 12 weeks (\pm 7 days).

* For Part 1b, all participants will stay at the clinic overnight on Day 1 after each dose. Optional overnight stay at the clinic on Day 2 and Day 3 after the first dose, i.e., on Day 2 and Day 3, participants can either stay at the clinic overnight or can be discharged after completion of the assessments and return the next morning for the subsequent assessments, at the Investigator's discretion.

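### Table 12 summarises HBsAg change by cohort at each timepoint with no cut-off, but visits after Day 169 are scheduled only for participants not yet back at baseline, so late cohort means can overstate how long the reduction lasts

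*Combined protocol and SAP*

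**What the plan says.** Section 9.4.5, Table 12 summarises HBsAg change by cohort with mean, SD, median, minimum and maximum, "in log10 IU/mL and % change from baseline) at each timepoint". It names no last timepoint and does not say how to treat participants who have finished. Its rows for HBsAg and HBeAg loss and seroconversion do fix a denominator, the PD analysis set; the change row does not.

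The visit rule is in the Schedule of Activities. For Part 2, Table 3 footnote a reads: "If HBsAg value does not return to baseline level on Day 169, participants will come to the clinic for additional follow-up visits". These visits come every 56 days "until HBsAg value returns to < 0.1 log below baseline for two consecutive visits, or up to Day 393, whichever comes first". For Part 3, Table 4 footnote b applies the same rule, starting "If HBsAg value does not return to baseline level on Day 169 of the last treatment period". Section 4.3, Table 7 repeats it: "If HBsAg does not return to baseline level at follow-up Week 24, will have additional follow-up visits until returns to <0.1 log below baseline".

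Both schedules mark HBsAg in the additional-visits column. Section 4.2.3.1 states that "the main virological endpoint in this study relies on measuring HBsAg at timepoints defined in the SoA". Footnotes on other tests give an additional visit its own day number: "Required for Day 337 visit only" in Part 2 and "Required for Day 337 of the last treatment period only" in Part 3.

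**The concern.** The variable that decides who is measured after Day 169 is the variable being averaged. A participant who is back at baseline completes the study at Week 24 and contributes nothing later; one who is still suppressed stays in. A mean over attendees at a late visit is therefore a mean over people selected for a lasting response, although the table would present it as the cohort's value.

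What is at stake is how durability is read. Section 4.2.4 gives greater and more sustained HBsAg reduction as the aim of the higher doses in Part 2, and the late part of the curve is where a reader would look for it. A flat or slowly rising late curve could partly reflect early returners having left the average.

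**Working it through.** The plan states no figure for this point, so there is none to reproduce. The check sets the visit rule against the summary rule and then works out what follows.

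**1. Late visit days.** Day 169 + 56 = 225, then 281, 337 and 393. Week 56 is 56 × 7 + 1 = Day 393, which agrees with the limit in Table 3. In Part 3 the days count from the last dose.

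**2. Who attends.** Entry depends on Day 169 HBsAg alone. Exit depends on two consecutive later values. Both remove participants near baseline, so they push in the same direction. Early-termination and virological-breakthrough samples do not bring back someone who completed at Day 169, and the optional post-study sample is for ADA and PK only.

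**3. Effect on the mean.** Inputs: cohort size 6 (Section 9.2); k participants have returned; attendees average m; returned participants have true value r.

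- Mean shown = m.
- Full-cohort mean = [(6 - k)m + kr]/6.
- With r = 0 the ratio of shown to full is 6/(6 - k).

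For an assumed m = -0.40 log10:

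| k | Shown | Full cohort, r = 0 | Ratio, r = 0 | Full cohort, r = -0.1 |
|---|---|---|---|---|
| 0 | -0.40 | -0.40 | 1.0 | -0.40 |
| 1 | -0.40 | -0.33 | 1.2 | -0.35 |
| 2 | -0.40 | -0.27 | 1.5 | -0.30 |
| 3 | -0.40 | -0.20 | 2.0 | -0.25 |

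On the percentage scale, -0.40 log10 is 10^(-0.40) - 1 = -60%. If all attendees have that value and k = 3 have returned to exactly baseline, the table shows -60% and the full-cohort mean is -30%. With k = 0 the entry rule causes no distortion.

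**4. Effect on the median.** If all attendees are at -0.40 and the rest at 0, the full-cohort median stays at -0.40 for k = 1 or 2 and becomes -0.20 for k = 3. The median may move little until about half the cohort has returned.

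**5. What a simulation can add.** All inputs are assumed:

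- cohorts of 6 with linear rebound, from dosing or from a Day 15 nadir;
- lognormal return time with median 140 to 280 days and CV 30% or 50%;
- assay SD 0 or 0.1 log10;
- entry if the Day 169 value is at least 0.1 log below baseline.

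For a 1.5 log10 drop, the Day 225 gap between full-cohort and attendee means ranges from 0.02 to 0.12 log10. The largest case shows -0.25 against -0.13. That maximum depends on the drop: it is 0.09, 0.12, 0.18 and 0.24 log10 for drops of 1.0, 1.5, 2.5 and 3.5. If HBsAg instead holds and then returns over 60 days, the gap for a 1.5 log10 drop reaches 0.31. None of these is a bound.

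**6. Open detail in the visit rule.** Entry states no tolerance; exit uses 0.1 log at two visits. If entry uses the same margin, the earliest completion by the exit rule is Day 281. If any value below baseline enters and Day 169 can be the first of the two visits, completion at Day 225 is possible. This changes timing and size, not direction.

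**The case against.** The strongest objection is that Table 12 never says its timepoints include the conditional visits. In the schedule grids these are one column, every 56 days, without the day and hour labels given to Days 1 to 169. The footnotes that mention Day 337 concern other tests, such as AFP and ultrasound. This stands in part: inclusion is the natural reading, not an explicit one. Nothing excludes the visits either, and HBsAg is collected at them, so the wording needs settling.

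Second, the list of statistics in Table 12 is not exhaustive, and n per visit may well be shown. That would reveal a shrinking denominator but not that attendance depends on the outcome.

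Third, a reader might infer that dose escalation, regimen choice or the ranking of doses would be distorted. The documents do not support that. Escalation rests on 28-day data (Section 4.1.1.1), outputs are descriptive (Section 9.4), and no section ties a decision to cohort means after Day 169. Section 9.4.6 addresses future regimens through exploratory PK/PD modelling, if considered appropriate. Because attendance is scheduled on observed HBsAg, a likelihood model of individual data can largely accommodate it. In the simulation with a 1.5 log10 drop, differences between cohorts at Day 225 moved by at most about 0.04 log10 under linear rebound and 0.13 under hold-then-return.

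Fourth, a reader might carry the concern over to Table 13. The same attendance rule applies there, but selection is on HBsAg, and no bias in those markers has been shown.

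**Conclusion.** The point holds as a minor one. On the natural reading of Table 12, cohort means of HBsAg change after Day 169 are taken over participants selected for not having returned, and they lean toward longer-lasting reduction if anyone has returned and stays near baseline. Medians follow if enough have returned. The direction rests on the visit rule and on that condition.

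The size is unknown, because the documents give no rebound curve or expected return times. The ratio 6/(6 - k) is exact only for returned participants at exactly baseline. It would be tempting to infer that the gap is about the protocol's 0.1 log margin or less. That is not supported: the 0.12 log10 linear maximum at Day 225 holds only for an assumed 1.5 log10 drop.

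Summaries through Day 169, the loss and seroconversion proportions on the PD set, and escalation decisions are not affected.

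**What to change.** In the HBsAg change row of Table 12, limit by-timepoint cohort means and medians to visits scheduled for all participants, that is, through Day 169 after the last dose. Show later visits as individual profiles, with the number attending and a footnote that attendance depends on HBsAg not having returned to baseline.

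A time-to-return summary over the full PD set would describe durability for everyone, but it is optional. If added, it should say whether return means one visit or the protocol's two consecutive visits. Table 13 need not change on grounds of bias.

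The cost is a change of analysis wording, a footnote and a change of display, with no new visits or data. The downside is that no cohort mean curve is shown after Day 169, even for a cohort in which nobody has returned and the mean would be sound.
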